3. OBJECTIVES AND ENDPOINTS

Objectives	Endpoints
Primary	*
To evaluate the safety, and tolerability of mepolizumab in participants with severe refractory asthma with elevated eosinophils	The primary estimand will be defined by the following: Endpoints: Incidence of on-treatment adverse events (AEs), serious adverse events (SAEs) and adverse events of special interest (AESIs)
	 Summary measure: Counts and percentages for incidence of at least one AE will be summarised overall, by system organ class and by preferred term
	 Population of interest: Severe refractory asthma patients in India with elevated eosinophils
	Key intercurrent events:Discontinuation of treatment (for any reason)
	 Strategy for intercurrent events: While on-treatment strategy will be used for treatment discontinuation. This will estimate the percentage of participants experiencing an AE, while receiving treatment. AEs will be defined as on-treatment between the first dose up to and including 28 days following the last dose of mepolizumab.
	A supplementary estimand will be defined using identical properties as for the primary estimand (summary measure, population of interest and key intercurrent events), however this supplementary estimand will report all AEs regardless of the discontinuation of study treatment. Endpoints: Incidence of AEs and SAEs
	 Strategy for intercurrent events: Treatment policy strategy will be used for treatment discontinuation. This summary will therefore be inclusive of all on-treatment and post-treatment AEs.
Secondary	
To evaluate the efficacy of mepolizumab in participants	The following secondary estimand is defined by the following:

Objectives	Endpoints
with severe refractory asthma	Endpoints:
with elevated eosinophils	 Number of clinically significant exacerbations (including exacerbations requiring hospitalization or ED visits) Number of exacerbations requiring hospitalization or ED visits Number of exacerbations requiring hospitalization Summary measure: Rate ratio comparing events/year during the 24-week follow-up period compared to the 12 months prior to screening Population of interest: Severe refractory asthma patients in India with elevated eosinophils Key intercurrent events: Discontinuation of treatment (for any reason)
	 Strategy for intercurrent events: Treatment policy strategy will be used for treatment discontinuation. This will estimate the treatment effect over the 24 week study period regardless of treatment discontinuation.

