8.1.1. Efficacy Endpoints

Primary Efficacy Endpoint

Not applicable

Secondary Efficacy Endpoint

- Number of clinically significant exacerbations
- Number of exacerbations requiring hospitalization or ED visits
- Number of exacerbations requiring hospitalization
- Change from baseline in clinic pre-bronchodilator FEV₁ at week 24
- Change from baseline in clinic post-bronchodilator FEV₁ at week 24
- Change from baseline in ACQ-5 score at week 24
- Change from baseline in morning PEF during weeks 20 24

8.1.2. Number of clinically significant exacerbations (including exacerbations requiring hospitalization or ED visits)

Clinically significant exacerbations of asthma as defined by:

Worsening of asthma which requires use of systemic corticosteroids and/or hospitalisation and/or Emergency Department (ED) visits.

¹For all subjects, i.v. or oral steroid (e.g., prednisone) for at least 3 days or a single IM CS dose is required. For subjects on maintenance systemic corticosteroids, at least double the existing maintenance dose for at least 3 days is required.

Clinically significant exacerbations of asthma will be defined as the worsening of asthma which requires use of systemic corticosteroids. Exacerbation will be treated per the investigator's clinical practice protocol with the use of oral or parenteral corticosteroids.

Clinically significant exacerbations recorded in the eCRF by the Investigator or designee will be verified using data from the eDiary to confirm that the exacerbation was associated with changes in peak flow, rescue medication use, nocturnal awakening due to asthma symptoms requiring rescue medication use or worsening of asthma symptom score. In the case that an event described as a clinically significant exacerbation is not associated with deterioration in at least one of these objective eDiary parameters, the investigator will be asked to provide an explanation to support the decision for defining the event as an exacerbation. In those circumstances where the event cannot be supported by any objective assessment, the case will not be included as a protocol defined exacerbation but will be included as an investigator defined exacerbation. This verification process will be overseen by GSK clinical staff to ensure consistency.

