For safety reasons alerts will be programmed into the eDiary to encourage the participant to contact the investigator if their asthma worsens (see Appendix 9). However, an alert in itself will not be classified as a clinically significant exacerbation.

8.1.3. Pulmonary Function Testing including Reversibility using the Maximum Post-Bronchodilator Method

Spirometry will be conducted, using the Spirometry equipment provided by GSK through a designated central laboratory at the visits specified in the Time and Events schedule. The spirometer should meet American Thoracic Society standards and produce a printout of all data generated, which should be stored in the participant's notes. The spirometer should be calibrated in accordance with the manufacturer's instructions and a calibration log maintained. Participants should withhold short-acting beta-2-agonists (SABAs) for ≥ 6 hours and LABAs for ≥ 12 hours prior to clinic visit. Assessments to be recorded will include FEV₁, and FVC.

Pre-bronchodilator measurements will be taken at baseline, week 8, 16, and 24. In addition, at visit specified in the Time and Events schedule, post-bronchodilator values will be recorded following reversibility testing, using the maximum post bronchodilator method. For participants unable to achieve ≥12% reversibility and 200mL change at Visit 1 (screening), reversibility can be repeated at Visit 2 (Week 0). The procedures to achieve the maximum post-bronchodilator are those generated by the Asthma Clinical Research Network. Further details of spirometry and reversibility testing procedures are presented in the SRM.

8.1.4. eDiary

The participant will be asked to record the following parameters daily in the eDiary from Visit 1 (screening) onwards:

- Morning peak flow (best of three), before rescue medication usage (L/min)
- Number of puffs of rescue usage over the previous 24-hours
- Asthma symptom score over the previous 24-hours using a 6-point scale (Appendix 8)
- Frequency of awakening due to asthma symptoms requiring rescue medication use.
 - Daily dose of OCS

The participant will be asked to complete the ACQ-5 weekly in the eDiary from Visit 1 (screening) onwards.

From Visit 1 (screening) to Visit 2 (Week 0) only, participants will record peak flow twice a day to allow for calculation of PEF diurnal variability.

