9.2. DEMOGRAPHIC AND BASELINE CHARACTERISTICS

Subjects' demographics and baseline characteristics will be summarized for the safety population.

Continuous variables (e.g., age and weight) will be summarized using descriptive statistics (n, mean, standard deviation, median, minimum, and maximum). Qualitative variables (e.g., sex and race) will

be summarized with counts and percentages.

The demographic parameters will include age, gender race height, weight and body mass index. Age will also be presented as a categorical variable (18-29 years, 30-49 years, 50-64 years and >=65 years). The baseline characteristics include:

- Asthma history and baseline disease characteristics which includes smoking history (never, current and former), age at onset (years) asthama diagnosis, time since diagnosis, asthma duration categories (1 to <5 years, 5 to <10 years, 10 to <15 years, 15 to <20 years, 20 to <25 years and >=25 years), experienced exacerbations in the previous 12 months, optimized OCS dose, duration of OCS dose prior to screening. Baseline optimized OCS dose also presented as a categorical variable (<7.5 mg/day, 7.5 to <15 mg/day, 15 to <30 mg/day and >=30 mg/day).
- Asthma exacerbations history which includes number of exacerbations (both descriptive and categorical), exacerbation types and causes of exacerbations in the previous 12 months.
- Family history of cardiovascular risk factors
- Past and current medical conditions
- Lung function test results at screening and baseline which includes pre- and post-bronchodilator FEV₁ (L), pre-bronchodilator percent predicted FEV₁ (%), pre-bronchodilator forced vital capacity (FVC) (L), reversibility (in mL and in %) and pre-bronchodilator FEV1/FVC.

By-subject listings of demographic and baseline characteristics will be provided for the safety populations.

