10.2. STATISTICAL METHODS FOR SECONDARY EFFIACACY ENDPOINTS

10.2.1. Asthma Exacerbations:

The number of clinically significant asthma exacerbations (including exacerbations requiring hospitalization or ED visits) that occur while on treatment will be analyzed using Negative Binomial regression using generalized linear model with a covariate of time period (pre-, post-mepolizumab as ordinal variable) with follow-up time within each period included as an offset within the model. The exacerbation rates during the pre- and post-treatment with mepolizumab will be presented, including comparison of pre- and post-mepolizumab exacerbation rates along with the with 95% confidence limits and corresponding p-value. Exacerbations separated by less than 7 days will be treated as a continuation of the same exacerbation. The following SAS code will be used:

where exbnum = number of clinically significant asthma exacerbations

period = pre- and post- mepolizumab treatment periods in which the exacerbation occurred logtime = \log_e (length of time in years in pre- mepolizumab and post- mepolizumab periods) Length of time (years) in study will be calculated as length of time (days)/365.25.

An unstructured covariance structure will be used in the model. If there are any convergence issue, then an alternative exchangeable or compound symmetric, autoregressive (AR (1)), Toeplitz covariance structure will be used. The variance of the mean estimate will be corrected for within-subject correlation by using REPEATED statement for subject in the GENMOD procedure.

The period of time for which exacerbation information will be included in the post-mepolizumab period will be from the start of treatment until the week 24 visit, regardless of treatment discontinuation. For

those participants with premature study withdrawal, the time period will include from the start of treatment until the date of withdrawal. Missing data (following early withdrawal) will be assumed to be missing at random (MAR) following subject withdrawal from the study.

In addition, a similar analysis will be conducted for frequency of exacerbations requiring hospitalization or ED visits and frequency of exacerbations requiring hospitalization if there are enough subjects in the corresponding category.

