APPENDIX 4. CLINICALLY SIGNFICANT EXACERBATIONS

Clinically significant exacerbations of asthma is defined as the worsening of asthma, which requires use of systemic corticosteroids. Exacerbations will be treated per the investigator's clinical practice protocol with the use of oral or parenteral corticosteroids.

Clinically significant exacerbations recorded in the eCRF by the Investigator or designee will be verified using data from the eDiary to confirm that the exacerbation was associated with changes in peak flow, rescue medication use, nocturnal awakening due to asthma symptoms requiring rescue medication use or worsening of asthma symptom score. In the case that an event described as a clinically significant exacerbation is not associated with deterioration in at least one of these objective eDiary parameters, the investigator will be asked to provide an explanation to support the decision for defining the event as an exacerbation. In those circumstances where the event cannot be supported by any objective assessment, the case will not be included as a protocol defined exacerbation but will be included as an investigator defined exacerbation. This verification process will be overseen by GSK clinical staff to ensure consistency.

For safety reasons alerts will be programmed into the eDiary to encourage the participant to contact the investigator if their asthma worsens. However, an alert in itself will not be classified as a clinically significant exacerbation.

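### eDiary verification can reclassify on-study exacerbations but not those in the comparator year, which taken alone can pull the pre/post rate ratio towards benefit

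*Protocol*

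**What the plan says.** **Comparison.** The secondary exacerbation estimand in Protocol section 3 is a within-participant contrast: "Rate ratio comparing events/year during the 24-week follow-up period compared to the 12 months prior to screening". There is no control arm.

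**Check on study.** Protocol section 8.1.2 states: "Clinically significant exacerbations recorded in the eCRF by the Investigator or designee will be verified using data from the eDiary". The diary measures are peak flow, rescue use, night-time awakening needing rescue medication, and symptom score. If none worsened, "the investigator will be asked to provide an explanation to support the decision for defining the event as an exacerbation". Only an event that still has no objective support changes class: "In those circumstances where the event cannot be supported by any objective assessment, the case will not be included as a protocol defined exacerbation". SAP Appendix 4 repeats the rule and says where such an event goes: "the case will not be included as a protocol defined exacerbation but will be included as an investigator defined exacerbation". Sponsor clinical staff oversee the process.

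**When diary data exist.** Protocol section 8.1.4: "The participant will be asked to record the following parameters daily in the eDiary from Visit 1 (screening) onwards". The Schedule of Activities has the device dispensed at Visit 1.

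**Comparator year.** The Schedule of Activities collects asthma and exacerbation history at Visit 1. SAP 9.2 describes what is summarised: "Asthma exacerbations history which includes number of exacerbations (both descriptive and categorical), exacerbation types and causes of exacerbations in the previous 12 months". Neither document gives a case definition or a verification step for these historical events.

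**Model.** SAP 10.2.1 fits a negative binomial model to the number of clinically significant exacerbations, with period (pre, post) as covariate and log time as offset. It adds: "Exacerbations separated by less than 7 days will be treated as a continuation of the same exacerbation". The rate analyses listed in SAP Appendix 5 cover clinically significant events, events needing hospitalisation or an ED visit, and events needing hospitalisation. None adds back investigator-defined events.

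**The concern.** In a single-arm before/after comparison, the ratio means something only if the same kind of event is counted in both periods. Here one period passes through a check that can take events out of the protocol-defined class. The check cannot add any, since the protocol says a diary alert does not itself count as an exacerbation. The other period has no such check and cannot have one.

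If the modelled on-study count is the protocol-defined one, part of any fall in rate could reflect a change of case definition rather than a change in disease. The trial is open-label, and no independent committee makes the classification. The exacerbation ratio is the main efficacy contrast in a study run because the Indian regulator asked for local data, so a reader will want to know how much of it comes from the check.

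**Working it through.** **Figures in the plan.** The documents give no exacerbation rate, rate ratio or expected share of events failing verification, so there is no stated figure to reproduce on this point. The sample-size table concerns adverse events only and does not bear on it.

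**Notation.**
- R = ratio of on-study to historical rate when no event is filtered in either period.
- f = share of on-study events reclassified as investigator defined (not given; assumed).
- g = share of historical events that the same check would have reclassified (cannot be known).
- c = share of true historical events captured in the Visit 1 history (not given; assumed).

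**Step 1: effect of filtering one period.**
- Neither period filtered: R.
- Both filtered: R × (1 − f)/(1 − g), which equals R if f = g.
- Only the on-study period filtered: R × (1 − f).

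The third line applies if only protocol-defined events enter the post-mepolizumab count.

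| f (assumed) | R = 1.00 reads | R = 0.50 reads |
|---|---|---|
| 0% | 1.00 | 0.50 |
| 5% | 0.95 | 0.475 |
| 10% | 0.90 | 0.45 |
| 20% | 0.80 | 0.40 |

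**Step 2: what this means in events.** Assume 100 participants, 2 events per year in both periods and 168 days on study. Expected on-study events are 100 × 2 × 168/365.25 = 92.0. At f = 10%, about 9 events across the whole trial are reclassified. The on-study rate becomes 82.8/(100 × 168/365.25) = 1.80 per year, and 1.80/2.00 = 0.90.

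**Step 3: effect on the interval.** A simulation with no true change used 100 participants, a between-subject gamma variance of 0.5, 168 days on study, and a period-only log rate ratio with robust within-subject variance. It gave the chance that the 95% interval lies wholly below 1:

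| Assumed rate per year | f = 0% | f = 10% | f = 20% |
|---|---|---|---|
| 1 | 3% | 9% | 21% |
| 2 | 3% | 12% | 37% |
| 3 | 2% | 17% | 52% |

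The median ratio was close to 1 − f throughout.

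**Step 4: incomplete history.** If the history captures only a share c of true events, the factor on R becomes (1 − f)/c.

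| | c = 100% | c = 90% | c = 80% |
|---|---|---|---|
| f = 10% | 0.90 | 1.00 | 1.125 |
| f = 20% | 0.80 | 0.889 | 1.00 |

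The two errors cancel at f = 1 − c. Beyond that point the net error works against mepolizumab.

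**Step 5: which class is modelled.** SAP 10.2.1 names the count as clinically significant exacerbations. The SAP defines that term only in Appendix 4, which includes the verification rule. Protocol-defined events are therefore the natural reading, but no sentence says so. If investigator-defined events are included, the factor in Step 1 is 1.00.

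**The case against.** **Events are reclassified, not discarded.** A reader might infer that unsupported events vanish. They do not. The investigator is asked first, a lack of diary deterioration is not enough by itself, and a reclassified event is kept under another label. SAP 10.2.1 also tabulates participants with any exacerbation separately from those with a clinically significant one, and Listing 16.2.6.2 lists exacerbations. This stands. However, the planned table covers the treatment period only and gives no rate ratio, so it does not show what the check does to the pre/post contrast.

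**The net direction is unknown.** A reader might infer that the reported ratio is biased towards benefit. Only the effect of this one mechanism, taken alone, has a known sign. History collected without a stated definition or source may miss events, and Step 4 shows that modest under-recording cancels or reverses the effect. An unmeasured opposing error is still no reason to leave this one unmeasured.

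**The 7-day rule.** A reader might infer that merging is also one-sided. The sentence sits in the description of the pre/post model and is not limited to on-study events. Whether the history carries dates that allow merging is not stated.

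**Sparse diaries.** It is tempting to say that participants with poor diary completion lose the most events. Neither document says how missing diary data are treated in verification, so this remains conjecture.

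**Hospitalisation and ED endpoints.** Objective support is plausibly easier to find for these, so f may be smaller there. The assumed range should not be read across all three endpoints.

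**Limited consequence.** The endpoint is secondary, no formal hypothesis is tested and p-values are nominal. The primary safety objective and the sample size are unaffected.

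**Conclusion.** The point holds in a limited form. Verification reaches only the on-study period, and the comparator year cannot be verified in the same way. On the natural but unstated reading of SAP 10.2.1 with Appendix 4, this multiplies the ratio by (1 − f): 0.95 to 0.80 for an assumed f of 5% to 20%, and no effect if f is zero. The documents supply neither f nor the completeness of the history, so they do not support a claim that the final ratio overstates benefit. They do support two narrower statements: the SAP leaves the modelled event class unnamed, and no planned analysis shows how far verification drives the ratio. This is worth correcting before database lock, at the level of a secondary endpoint with nominal inference.

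**What to change.** In SAP 10.2.1:

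1. State whether the modelled on-study count is protocol-defined events only, or protocol-defined plus investigator-defined events.
2. Run the same pre/post model with all investigator-recorded on-study events that meet the treatment-based definition in Protocol section 8.1.2, whether or not the eDiary check supports them. Present this ratio beside the verified-event ratio. The verified definition need not be dropped.
3. Report the number of on-study events reclassified.
4. State the definition used for historical events.
5. Apply the merging rule for events less than 7 days apart to the history where event dates exist, and note the limitation where they do not.

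The cost is SAP wording and one extra model run, because both event classes are already to be recorded. The downside is that the added ratio may be less favourable than the verified one. It also does not correct incomplete history, which remains a limitation to state in the report.

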8.1.5. Asthma Control Questionnaire-5 (ACQ-5)

The ACQ-5 is a five-item questionnaire, which has been developed as a measure of participants' asthma control that can be quickly and easily completed in clinical practice (Juniper, 2005). The questions are designed to be self-completed by the participant. The five questions enquire about the frequency and/or severity of symptoms (nocturnal awakening on waking in the morning, activity limitation, and shortness of breath, wheeze). The response options for all these questions consist of a zero (no impairment/limitation) to six (total impairment/ limitation) scale. The ACQ-5 score is a mean of the values recorded for the individual questions.

Throughout the study participants should complete the ACQ-5 on a weekly basis using their eDiary.

The participant should complete the questionnaire within the eDiary. The participant should be instructed to complete the questions as accurately as possible. The participant should be reassured that there are no right or wrong answers. If the participant requests help or clarification with any of the questions, he/she will be asked to re-read the instructions and give the answer that best reflects how he/she felt over the previous week. The investigator should not provide the participant with any answer or attempt to interpret any portion of a question.

If the ACQ-5 is completed through the eDiary while the participant is at a scheduled in clinic Visit, it is recommended that the ACQ be administered at the same time during the visit. To avoid biasing responses, the participants should not be told the results of diagnostic tests prior to completing the questionnaire and should be completed before any procedures are performed on the participant to avoid influencing the participants' response. Adequate time should be allowed to complete all items on the ACQ.

